7.3.1.2. Secondary analysis

Target PPS

population:

Analysis Same as primary analysis. However, stratification analysis using the content: stratification factors is not conducted.

### 7.3.2. Analysis of secondary endpoints

Target FAS, PPS

population:

Analysis 1) Regression rate at 24 weeks after the first dose

content: The same analysis as the primary and secondary analyses of the primary endpoint is conducted.

2) HPV E7-specific immune response is calculated for FAS and PPS for each group at 16 and 24 weeks after the first dose:

The 95% confidence interval is also calculated using the Clopper–Pearson method. Furthermore, the same analysis is conducted by stratification according to the stratification factors for FAS.

3) Change in HPV16 E7 molecule protein expression level (relative quantification value)

For FAS and PPS, summary statistics are calculated by group for the HPV16 E7 molecule protein expression level before the first administration, at 16 and 24

weeks after the first dose, as well as for the magnitude and rate of change at 16 and 24 weeks after the first dose. Furthermore, comparisons of the magnitude and rate of change between each dose group and the placebo group are conducted using the Wilcoxon rank sum test. The same analysis is conducted for FAS by stratification using the stratification factors. Additionally, for FAS and PPS, a spaghetti plot of HPV16 E7 molecule protein level is created for each group, from the first administration of the trial drug in each subject to weeks 16 and 24.

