- When the protocol was revised to Ver. 2, the permitted range for subject visits was changed; however, this change was not reflected in the analysis plan. Therefore, the range of data adoption for the evaluation periods (Section 6.4.4) was changed to reflect the permitted range of visits in the protocol.
- When the protocol was revised to Ver. 5 of this protocol, we clarified the regulations regarding histology at week 24 for cases judged to be normal at week 16. Separately, we stipulated that follow-ups up to 24 weeks would be conducted according to the diagnosis by the attending physician at the facility 16 weeks after the first dose, except for cases judged to be CIN3 requiring treatment or invasive cancer. However, this content was not reflected in this analysis plan. Therefore, the above items were added to the primary endpoint (Section 4.1.1), and the handling of missing values (Section 6.5) was revised to reflect this content.

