#### 3. Trial method

#### 3.1 Trial design

The trial was a placebo-controlled randomized double-blind comparative study (Phase I/II clinical trial) of four dose parallel groups: placebo, low-dose (0.5 g/administration/day), intermediate-dose (1.0 g/administration/day), and high-dose (1.5 g/administration/day).

- Dosage and dose: The subject will take three sticks of trial drug once daily before breakfast. Consecutive administration for five days constitutes one course, with a total of four courses administered from the first administration (Day 1 to Day 5), Day 8 to Day 12, Day 22 to Day 26, and Day 50 to Day 54. However, the dose on Day 1 will be administered between meals in the hospital.
- Trial period: 16 weeks. Primary evaluation at 16 weeks after first dose.
- Follow-up period: eight weeks. Pathological evaluation (biopsy) was performed 16 weeks after the first dose to avoid missing patients who had progressed to invasive cancer; if the lesion was CIN3 or lower, the patients were again evaluated pathologically 24 weeks after the first dose. If a patient was diagnosed clinically as CIN3 or more at week 16, she received standard therapy.

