## Table 1 Observation / survey and test items during the trial (follow-up) period

1

Item	Eligibi	ility nation period	Trial p	Trial period									Follow-up period		
	Initia 1 visit	Administrati on start day Day 1	(Wee k 1)	(Wee k 2)	(Wee k 3)	(Wee k 4)	(Wee k 5)	(Wee k 6–7)	(Wee k 8)	(Wee k 9)	(Wee k 10–15 )	(Wee k 16)	(Wee k 17–23 )	(Wee k 24)	At discontinuati on
Visit															
Permitted range of visit															
Prescription of trial drug															
Administratio n of trial drug															
Confirmation of drug administration status															
Consent acquisition															

Confirmation of selection / exclusion criteria								
Case registration								
HPV genotype test (for eligibility confirmation)								
HPV genotype test (central test)								
Histology (central pathological judgment)								
Histology (implementin g medical facility judgment)								
Histology								

Colposcopy								
Laboratory test								
Pregnancy reaction (serum hCG)								
HIV test								
HPV16E7 protein expression level								
E7 protein expression (cervical cells)								
HPVE7-specif ic immune response								
Subjective symptoms h / objective findings								

Concomitant drugs / therapies								
Confirmation of medical history and complications								
Confirmation of adverse events i								

 $\circ$ : Item that is implemented before the start of administration or confirms the test results;  $\bullet$ : Item that is implemented after the start of administration;  $\triangle$ : Item that is implemented in case of suspected invasive cancer;  $\bigcirc$ : Item that is implemented only on cases judged to be applicable in the follow-up survey at 16 weeks after administration

a: Implement test for selection/exclusion criteria confirmation after consent

b: Confirm eligibility based on applicable data in case there is data within 90 days prior to consent (data at another hospital, in-hospital data not required). Implement the test after consent in case there is no applicable data.

c: Implement test using E7 protein expression specimen collected on the same day

d: Confirm no problem with the test results (no possibility of pregnancy) before prescription of the trial drug. Administration of the trial drug shall start within 10 days from the day when the applicable laboratory test was conducted.

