#### 4.1.2 Secondary endpoints

1) Regression rate at 24 weeks after the first dose

2) HPV E7-specific immune response: before trial drug administration, 16 and 24 weeks after the first dose.

The presence or absence of HPV E7-specific immune response at 16 weeks after the first dose and at 24 weeks after the first dose will be used as an endpoint. Separately, the presence or absence of HPV E7-specific immune response prior to the first dose will be used as a stratification factor for stratified analysis.

3) Change in HPV 16 E7 molecule protein expression level: at 16 and 24 weeks after the first dose.

HPV 16 E7 molecule protein expression level will involve measurements of the expression level (copy/ng) by relative quantification before first administration of the trial drug, and at 16 and 24 weeks after the first dose. The expression level by absolute quantification will also be measured only before the first administration of the trial drug. The magnitude and rate of change of the expression level (relative quantification value) from before first administration to 16 and 24 weeks after the first dose will be the endpoint. Separately, the expression level (absolute quantitative value) before the first dose is used as a stratification factor for stratification analysis. For this stratification factor, two categories of "below median" and "above median" and three categories of "below first tertile," "above first tertile, below second tertile," and "above second tertile" will be used.

4) Improvement in cytology\* of HSIL/CIN 2-3 lesions: at 16 and at 24 weeks after the first dose. Changes in lesions in cytology are judged by any of the following in subjects diagnosed with HSIL at the time of registration.

PR: Change to LSIL, ASC-US, or NILM

SD: No change from HSIL

PD: Change to SCC

NE: Change to AGC or ASC-H

\* Cytology: Cytological tests of the cervix will be conducted before trial drug administration, nine weeks after the first dose, 16 and 24 weeks after the first dose.

5) Percentages of "CR," "PR," "SD," and "PD" in the pathological improvement indicators of cervical intraepithelial neoplasia lesions: at 16 and 24 weeks after the first dose.

6) Presence or absence of changes in the HPV16: at 16 and 24 weeks after the first dose.HPV genotype test: conducted before trial drug administration, 16 and 24 weeks after the first dose (applicable cases only) to measure the HPV genotype.

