6.4.4 Range of data adoption for evaluation periods

Table 2 shows the trial protocol-stipulated evaluation periods and the corresponding time intervals of the efficacy endpoints of histology, cytology, presence or absence of an HPV E7-specific immune response, and HPV genotype changes, as well as the safety endpoints of laboratory tests. In practice, the tests may be conducted at a time point outside the defined time interval. Therefore, the range of data adoption is defined in the rightmost column of Table 2, and the following two points are set as the policy for setting the range of data adoption in such cases:

1) For the four visits at weeks 5, 9, 16, and 24, for which laboratory test measurements are planned, there should be no overlap in the two ranges of data adoption that correspond to two adjacent visits, and no gaps in time.

2) For weeks 5, 9, and 16, the upper limit of the range of data adoption should be one week after the last day of the permissible range of visits (e.g., for week 5, the range should be until day 49, which is one week after day 42, i.e., the last day of that week).

The data obtained within the range of data adoption should be adopted as the data of the corresponding visit. For example, if histology was conducted within the range of day 85–day 133, then the results will be adopted as data at the end of the trial (16 weeks after first administration).

Evolution	Time interval	Test item		Danga	f data		
period	(according to	Histology	Cytology	HPV*	Laboratory	adoption	i data
_	clinical trial				test		

Table 2. Trial protocol-stipulated evaluation period and range of data adoption

	protocol)					
First visit		0	0			~ Day1
Administration	Day 1			0	0	~ Day1
start day						
Week 1	Day 2–7					
Week 2	Day 8–14					
Week 3	Day 15–21					
Week 4	Day 22–28					
Week 5	Day 29–42**				•	~ Day 2–49
Week 6–7	Day 36–49					
Week 8	Day 50–56					
Week 9	Day 57–77**		•		•	~ Day 50–84
Week 10–15	Day 64–105					
Week 16	Day	•	•	•	•	~ Day 85–133
	106-126**					
Week 17–23	Day 113–161					
Week 24	Day	0	0	0	0	~ Day 134
	162–182**					
At		•	•	•	•	
discontinuation						

\* HPV: HPVE7-specific immune response, HPV genotype

\*\* : Permissible range of visit

 $\circ$ : Implemented before start of administration;  $\bullet$ : Implemented after start of administration;  $\odot$ : Implemented only for cases subject to follow-up survey

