#### 6.5 Handling of missing values

As a general rule, missing data will not be supplemented. However, as described in Section 4.4.1, the implementation of histopathological tests at 24 weeks after the first dose (applicable cases only) for cases judged to be normal at 16 weeks after the first dose is also stipulated in cases where CIN lesion is confirmed by colposcopy. Based on these points, handling will be as follows: (1) In the cases judged to be "normal" at 16 weeks after the first dose, the data of "at week 24" will be handled as normal. (2) In the cases judged to be "CIN3" at 16 weeks after the first dose, the data of "at week 24" will be handled as CIN3. (3) In the cases with missing histopathological tests at 16 weeks after the first dose will be handled as missing data.

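### The week-24 test of E7 change compares only women kept in follow-up on their week-16 diagnosis, so it is not a randomised comparison and can be distorted, usually toward no difference or against the drug

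*SAP*

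**What the plan says.** **Endpoint and test.** SAP section 4.1.2 item 3 defines the endpoint as the magnitude and rate of change in E7 expression (relative quantification) "from before first administration to 16 and 24 weeks after the first dose will be the endpoint". Section 7.3.2 item 3 states that "comparisons of the magnitude and rate of change between each dose group and the placebo group are conducted using the Wilcoxon rank sum test", in the FAS and the PPS, and repeats the analysis by stratum in the FAS. It does not distinguish week 24 from week 16.

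**Who is measured at week 24.** Section 1.2 says that follow-up to week 24 goes by the attending physician's diagnosis at the facility at week 16, "except for cases judged to be CIN3 requiring treatment or invasive cancer". The Table 1 legend has a symbol for an "Item that is implemented only on cases judged to be applicable in the follow-up survey at 16 weeks after administration", and the Table 2 legend in section 6.4.4 has a matching one: "Implemented only for cases subject to follow-up survey". Table 2 has no column for E7 protein. The cell symbols of Table 1 are not legible in the text available here, so the week-24 restriction for E7 is read from the legend and the follow-up rule.

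**Which CIN3 cases leave.** Section 3.1 gives two statements. One is "if the lesion was CIN3 or lower, the patients were again evaluated pathologically 24 weeks after the first dose". The other is "If a patient was diagnosed clinically as CIN3 or more at week 16, she received standard therapy".

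**Missing data.** Section 6.5: "As a general rule, missing data will not be supplemented". Its exceptions concern week-24 histology: a week-16 normal stays normal and a week-16 CIN3 stays CIN3. E7 has no corresponding rule.

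**The concern.** Randomisation makes the arms comparable at entry. It does not make comparable the women who remain after a selection that treatment can influence. On placebo, the women measured at week 24 are those whose lesions were mild or regressed spontaneously. On an effective dose they are those women plus any who stayed because the drug worked. If E7 change goes with lesion change, the placebo set is the more favourably selected of the two, and the E7 contrast is pulled down on the active side.

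Many women could be affected. Section 3.3 plans 41 per group with 10 CIN2 cases, so 41 - 10 = 31 (31/41 = 76%) enter with CIN3. The SAP gives the week-24 p-value the same standing as the week-16 one, with no caveat.

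The week-24 tables in section 7.3.3 items 3, 5, 6 and 7 have a related defect. A woman who left with CIN3 keeps a week-24 histology category under section 6.5 (SD if she entered with CIN3, PD if she entered with CIN2) but has no week-24 biomarker value. The biomarker figures in those categories, and under non-response in items 3, 5 and 6, then describe only the women who stayed.

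**Working it through.** The SAP states no expected E7 effect, leaving rate or E7-histology correlation, so there is no figure of the plan's own to reproduce. The check is a sensitivity calculation.

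**From the SAP:** 41 per arm (section 3.3); two-sided 0.05 (section 6.1); Wilcoxon rank sum test (section 7.3.2).

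**Assumed:** a normal latent week-16 histology improvement L, in SD units. A woman stays if L exceeds a cut-off c common to the arms. The drug shifts L by dL and E7 improvement by dE, and the within-arm correlation of the two is r. Leaving rates, placebo/active, are 50/30%, 60/40% and 40/25%.

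**Formulas.** c = z(placebo leaving rate) and dL = c - z(active leaving rate), where z is the normal quantile. With λ(x) = φ(x)/(1 - Φ(x)), selection raises mean L among stayers by λ(c) on placebo and by λ(c - dL) on active. The gap is G = λ(c) - λ(c - dL). The E7 difference among stayers is dE - r·G, so the share lost is r·G/dE.

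| Leaving, placebo/active | dL | λ(c) | λ(c - dL) | G | G/dL |
|---|---|---|---|---|---|
| 50/30% | 0.524 | 0.798 | 0.497 | 0.301 | 57% |
| 60/40% | 0.507 | 0.966 | 0.644 | 0.322 | 64% |
| 40/25% | 0.421 | 0.644 | 0.424 | 0.220 | 52% |

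**Share of the E7 difference lost**
- r = 0: none. Only numbers are lost.
- E7 shifted by as many SD as histology (dE = dL): loss = r × G/dL. At r = 0.5 this is 29%, 32% and 26% for the three rows; at r = 0.7 it is 40%, 44% and 37%.
- E7 effect wholly through the lesion (dE = r·dL): r cancels and the loss is G/dL = 57%, 64% and 52%.

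**Histology effect but no E7 effect (dE = 0).** The stayers' difference is -r·G. At 50/30% that is -0.15 SD at r = 0.5 and -0.21 SD at r = 0.7, against the drug. In simulations with a histology shift of 0.62 SD, 30-60% of placebo women leaving and r from 0.3 to 0.7, the spurious difference was 0.08-0.27 SD. The nominal 5% test rejected in 5-15% of runs.

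**No effect on either outcome.** Simulated rejection was 4.4-4.5%, so the level holds.

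**Power.** At 50/30% leaving, r = 0.7 and the E7 effect wholly through the lesion, simulated Wilcoxon power is about 37% with all 41 per arm. It is 21% after random loss to the same numbers and about 9% among stayers. Of the 37 - 9 = 28 points lost, 37 - 21 = 16 come from smaller numbers and 21 - 9 = 12 from selection.

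**The case against.** **The tempting stronger reading.** A reader might infer that the week-24 test removes most of any real effect, or that selection alone takes power from about 37% to 9%. The SAP supports neither. The 52-64% loss needs the drug to act on E7 only through lesion response, and more than half of that power drop is sample size. The direction is not fixed either: under the settings above a true E7 effect shrinks but keeps its sign, and a difference against the drug appears when histology responds and E7 does not.

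**The exit rule may be looser than modelled.** Section 1.2 removes only CIN3 requiring treatment, and one statement in section 3.1 has CIN3 re-evaluated at week 24. Selection also runs on the facility diagnosis, which Table 1 lists separately from the central pathological judgment, so a sharp cut-off on the histology outcome itself is a simplification. Both points stand and would weaken the bias. They would not remove it unless essentially every week-16 CIN3 or cancer case were measured at week 24, which section 1.2 rules out.

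**The consequence is limited.** This is one later time point of one secondary biomarker, section 6.2 disclaims multiplicity control for secondary endpoints, and section 4.1.1 rests the recommended dose on regression rates. The exploratory tables carry no tests. All of this stands, and it makes the point a cheap improvement rather than a threat to the trial's main result.

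**The all-women benchmark is a choice.** After standard therapy a week-24 E7 value no longer reflects trial drug alone. That is fair, and it argues for describing week 24 rather than for rescuing a test there.

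**Conclusion.** The point holds as a structural one. As written, the week-24 E7 test conditions on a post-randomisation outcome that the drug is meant to change, and the SAP gives no restriction, caveat or sensitivity analysis for it. When the drug affects histology and E7 change correlates with histology, the comparison can be distorted, usually toward no difference or against the drug.

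The size is conditional. The loss runs from nothing to about two thirds of the difference according to the correlation and how far the E7 effect runs through the lesion. Those inputs and the leaving rates are assumptions, not SAP figures. With no effect on either outcome the test is valid, and the week-16 comparison of the same endpoint is untouched by this selection.

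**What to change.** 1. In section 7.3.2 item 3, restrict the between-group Wilcoxon test to week 16.
2. At week 24, give summary statistics by arm without p-values, labelled as subjects remaining in follow-up. Add the number per arm not measured and their week-16 histology.
3. In the week-24 tables of section 7.3.3 items 3, 5, 6 and 7, show cases with carried-forward histology separately from those with a week-24 reading.
4. Reconcile sections 1.2 and 3.1 on which week-16 CIN3 cases are followed to week 24, so that the subset can be described exactly.

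This is wording only and needs no new data. The cost is that the week-24 E7 p-values are dropped. A worst-rank test that scores the women who left as worst would bring them back in, but week-16 histology would then largely drive an E7 test. It is not needed here.

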#### 4) Effect of HSIL/CIN 2-3 lesions on cytology

For FAS and PPS, for subjects diagnosed with HSIL at registration, the percentages of "PR," "SD," "PD," and "No judgment" are calculated for each group at weeks 16 and 24. The denominator of the percentage (%) of each judgment is the number of cases in the analysis set. Furthermore, for the FAS, the same tabulation is conducted by stratification using stratification factors.

5) Percentages of "CR," "PR," "SD," and "PD" in the histopathological evaluation indicators of cervical intraepithelial neoplasia

For FAS and PPS, the percentages of "CR," "PR," "SD," and "PD," and "No judgment" are calculated for each group at weeks 16 and 24. The denominator of the percentage (%) of each judgment is the number of cases in the analysis set. Furthermore, for the CR rate, Fisher's exact test is used for pairwise comparisons between each dose group and the placebo group. Additionally, the dose-response relationship is investigated with the same contrasts as in Section 7.3.1.1). For FAS, the same tabulation is conducted by stratification using the stratification factors.

6) Evaluation of changes in the HPV genotype

For FAS and PPS, the percentages of the number of cases for judgment categories ("negative," "positive, but not including type 16," "HPV16 only," "HPV16+other types," and "no judgment") are calculated for each group at weeks 16 and 24, with the number of cases for each judgment of "HPV16 only" and "HPV16+other types" before trial drug administration. Separately, the number and percentage of cases is calculated for the category of "clearance of HPV16" by merging "negative" and "positive, but not including HPV16." Furthermore, for FAS, the same tabulation is conducted by stratification using the stratification factors.

7) Disease control rate

For FAS and PPS, the percentage of subjects with histology of CIN3 at

registration improving to CIN2 or lower at weeks 16 and 24 is calculated for each group, and their 95% confidence intervals (Clopper–Pearson method) are calculated. Additionally, Fisher's exact test is used for pairwise comparisons between each dose group and the placebo group. Furthermore, for FAS, the same tabulation is conducted by stratification using the stratification factors.

Definition:

• For subjects diagnosed with HSIL at registration, the judgment categories for the effect of HSIL/CIN 2-3 in cytology are set as "PR," "SD," "PD," and "no judgment." Here, "no judgment" includes "NE" and missing judgment results because of tests not being conducted, etc.

• The judgment categories for pathological improvement indicators of cervical intraepithelial neoplasia are set as "CR," "PR," "SD," "PD," and "no judgment." Here, "no judgment" includes "NE" and missing judgment results because of tests not being conducted, etc.

• The judgment categories for HPV genotype are set as "negative," "positive, but not including HPV16," "HPV16 only," "HPV16+other types," and "no judgment." Here, "no judgment" includes missing judgment results because of tests not being conducted, etc.

• If either of the two time points is "NE" or the judgment result is missing, the judgment result at the other time point is set as the best effect. When a judgment result is not obtained at either of the two time points, the best effect is set as "no judgment."

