#### 1.2 Changes from trial protocol

This analysis plan (Ver. 2) is a revision of Ver. 1 (May 27, 2019). In Ver. 2, the following revisions have been made in accordance with the revisions from V8.0 (dated January 10, 2020) to V13.0 (dated March 9, 2022) of the trial protocol.

- The analysis target of evaluating the improvement in cytology of HSIL/CIN 2-3 lesions, which is a secondary endpoint, was changed.
- Analysis methods for the following three secondary endpoints were added: 1) change in HPV 16 E7 molecule protein expression level (relative quantification value) and 2) disease control rate.

Furthermore, the HPV 16 E7 molecule protein expression level (absolute quantification value) before the start of administration and the HPV E7-specific immune response before the start of administration were added as stratification factors for the stratification analysis. Additionally, the following were added as exploratory analyses.

- 1) Investigation of the distribution of E7 protein expression level (absolute quantification value) before first administration.
- 2) Investigation of the relationship between the E7 protein expression level (absolute quantification value) before first administration and the improvement effect of the trial drug.
- 3) Investigation of the relationship between changes in the E7 protein expression level (relative quantification value) after administration and pathological judgment.
- 4) Investigation of the relationship between the presence or absence of HPV E7-specific immune response before first administration and the improvement effect of the trial drug.
- 5) Investigation of the relationship between the presence or absence of HPV E7-specific immune response after administration and pathological judgment.
- 6) Investigation of the relationship between the HPV E7-specific immune response SFC value after administration and pathological judgment.
- 7) Investigation of the relationship between the log-transformed HPV E7-specific immune response SFC value after administration and pathological judgment.

Moreover, we found that the analysis plan (Ver. 2) did not accurately reflect the changes in the

revision items of the clinical trial protocol; therefore, the following items were revised in this analysis plan (Ver. 2.1).

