### 5. Analysis set

### 5.1 Full analysis set (FAS)

The FAS was a set in which the following cases were excluded from all registered cases:

1) Examples of serious GCP violations (breach of consent acquisition, breach of contract, non-deliberation by the IRB).

- 2) Cases violating eligibility criteria, cases unblinded by non-regular procedures.
- 3) Trial drug-naive cases.
- 4) Cases with no efficacy data.

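### The cytology percentages are confined to subjects with HSIL at registration, but the stated denominator is the FAS or PPS, which entry cytology does not limit

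*SAP*

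**What the plan says.** Three places in the SAP limit this endpoint to a subset of subjects.

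- Section 4.1.2, item 4) defines it: "Changes in lesions in cytology are judged by any of the following in subjects diagnosed with HSIL at the time of registration". PR, SD, PD and NE are all cytology results reached from an HSIL starting point.
- Section 7.3.2, item 4) repeats the limit for the FAS and PPS tables: "for subjects diagnosed with HSIL at registration, the percentages of" PR, SD, PD and no judgment are calculated by group at weeks 16 and 24.
- The definitions closing section 7.3.2 do so again: "For subjects diagnosed with HSIL at registration, the judgment categories for the effect of HSIL/CIN 2-3 in cytology are set as" those four. On the last of the four they add: "Here, 'no judgment' includes 'NE' and missing judgment results because of tests not being conducted, etc".

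The sentence after the calculation rule in item 4) fixes the denominator: "The denominator of the percentage (%) of each judgment is the number of cases in the analysis set".

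Section 5 defines the analysis sets. For the FAS: "The FAS was a set in which the following cases were excluded from all registered cases". Neither the FAS nor the PPS exclusions mention entry cytology as such.

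**The concern.** The subjects counted in the numerator and the subjects in the denominator are not the same population. A subject without HSIL cytology at entry cannot be PR, SD or PD. Nor does such a subject fall under no judgment, which is described as covering NE and missing results. As written, that subject adds one to the denominator and nothing to any category.

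The displayed percentage then depends on two things: how often HSIL cytology improved, and how many subjects in the arm entered with HSIL cytology. Only the first is of interest. The second is a baseline feature that is not an allocation factor (section 3.2 lists diagnosis, HPV genotype and facility), so it can differ between arms by chance. Item 4) plans no test or interval, so these percentages are all that the table offers for comparing arms.

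**Working it through.** **Reading the denominator.** The SAP gives no figure for this endpoint, so there is nothing to reproduce. Three comparisons bear on what the sentence means.

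- Item 5) (histology) uses the same denominator sentence. It fits there, because the histology categories apply to every subject.
- Item 7) (disease control) is also confined to a subset, CIN3 at registration. It has no whole-set denominator sentence and is worded as a percentage of that subset.
- Section 7.3.1.1 divides the primary rate by the number of FAS cases, so dividing by a full analysis set is the SAP's normal practice.

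**Inputs.**

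- n = 41 per arm (section 3.3: 164 in total, 4 × 41). Taking all 41 as analysed is an assumption.
- h, the share of an arm with HSIL cytology at entry: not given. Assumed range 0.5 to 1.0.
- p, the PR rate among those subjects: not given. Assumed 50% in the first example and 40% thereafter.

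**Formulas.** Displayed PR rate = h × p. Sum of the four categories = h. With an HSIL denominator, the PR rate is p and the sum is 100%, whatever h is.

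**Two arms with the same true rate.** With p = 50%: 0.55 × 0.50 = 27.5% and 0.70 × 0.50 = 35.0%, a gap of 7.5 points with no true difference. With p = 40% and whole subjects, 33 and 25 HSIL subjects of 41 give 0.40 × 33/41 = 32.2% and 0.40 × 25/41 = 24.4%, a gap of 7.8 points.

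**Range over h, with p = 40%.** The SD of the gap between two arms caused by the share alone is p × √(2h(1−h)/41). At h = 0.7 this is 0.40 × √(0.42/41) = 4.0 points. The last column is simulated: HSIL counts are drawn binomially at 41 per arm and the PR rate is held at 40% of each count, so it isolates the effect of the share.

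| h | Displayed PR | Four categories sum to (whole subjects) | SD of gap from share | Chance that at least one of three dose–placebo gaps is 5 points or more |
|---|---|---|---|---|
| 1.0 | 40% | 100% | 0 | 0 |
| 0.9 | 36% | 37/41 = 90.2% | 2.7 points | 11% |
| 0.8 | 32% | 33/41 = 80.5% | 3.5 points | 29% |
| 0.7 | 28% | 29/41 = 70.7% | 4.0 points | 40% |
| 0.6 | 24% | 25/41 = 61.0% | 4.3 points | 46% |

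At h = 0.5 the displayed rate would be 20% and the sum 20/41 = 48.8%.

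**Order of arms.** 12 of 24 against 13 of 32 HSIL subjects is 50.0% against 40.6%. Over 41 it is 29.3% against 31.7%, so the order reverses.

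**Set against ordinary sampling variation.** At h = 0.7, chance variation in PR itself contributes an SD of (29/41) × √(2 × 0.4 × 0.6/29) = 9.1 points to the displayed gap, compared with 4.0 from the share. The share adds avoidable noise but is not the main source of it. The shift in level, 28% shown for a true 40%, is systematic.

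**The case against.** The strongest reply is that the sentence should be read in context. It follows directly on the restriction to HSIL subjects, so the analysis set may mean those subjects within the FAS or PPS. Its purpose may simply be to keep no-judgment cases in the denominator. Strict literalism cannot be right anyway: it would divide each arm, and each stratum, by the whole FAS. This reading is possible, but the SAP nowhere states it, and the identical sentence in item 5) means the full set. Two programmers could produce different tables.

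A second reply is that the SAP labels every subject HSIL/CIN2 or HSIL/CIN3, so HSIL at registration need exclude nobody. Section 4.1.2 makes this a cytology endpoint scored in cytology terms, and if nobody were excluded the restriction would be needless. The cytology reading is therefore the likelier one, but the size of the excluded group is unknown and may be zero.

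A third reply stands in full. Section 6.3 calls for counts alongside percentages. The four counts sum to the number of HSIL subjects in the arm, so a reader can recompute the proper rate. Appendix 2 also plans a listing of individual efficacy responses. No information is lost.

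A reader might also infer from section 1.2 that Version 2 introduced the HSIL restriction and left an old denominator behind. That section says only: "The analysis target of evaluating the improvement in cytology of HSIL/CIN 2-3 lesions, which is a secondary endpoint, was changed". It does not say from what to what, so this history remains a guess and the point does not depend on it.

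**Conclusion.** The point holds conditionally. As worded, item 4) counts HSIL subjects and divides by a set not limited by entry cytology. If some analysed subjects lacked HSIL cytology at entry, the displayed rates equal the true rate times the HSIL share, fall short of 100% in total, and can differ between arms because the shares differ. The 7.5-point example rests on assumed inputs (50%, 55%, 70%), as does the whole range above.

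Two stronger conclusions are tempting. One is that every cytology rate in this trial is diluted. The SAP does not give the share, and at 100% there is no dilution. The other is that the trial's conclusions are at risk. This is a descriptive tabulation of one secondary endpoint, with no test, interval or contrast attached. The dose-response question in sections 4.1 and 7.3.1 rests on 16-week histology, which is unaffected. Severity is minor to moderate: a wording that can yield a misleading table and is easily put right.

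**What to change.** In section 7.3.2, item 4), replace the denominator sentence with one stating that each percentage is taken over the FAS (or PPS) subjects in that group who had HSIL on cytology at registration, with no-judgment cases kept in. For the stratified FAS tables, use the same count within the stratum. Print that number for each group and stratum.

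In section 4.1.2, item 4) and in the definitions of section 7.3.2, write HSIL on cytology, so that the term is not confused with the HSIL/CIN2 and HSIL/CIN3 diagnosis labels.

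The cost is one replaced sentence, a small wording change in two other places and one denominator in the program. No new data are needed. If all analysed subjects prove to have had HSIL cytology at entry, the table is unchanged.
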